### 3. Background/Rationale & Purpose

#### 3.1 Background Information

**Description of the health issue and research question.** Significant disparities exist in access to mental health services for low income and ethnically diverse children. On average, low income and minority children are diagnosed later than their white, higher income peers, and experience substantial delays in initiating treatment – even after diagnosis. Obtaining a diagnosis and engaging with treatment involves a number of complex steps, including: visits to primary care for screening, visits to a subspecialist for diagnosis, receipt of an individually-tailored treatment plan, and ongoing specialty support. Common barriers include availability of services, miscommunication, complex payment systems, and cultural bias. In addition, because children require coordination of the entire family unit across many systems (school, medical, community), unique challenges (e.g., parent stress, parent-provider communication) also exist for this population. Therefore, an individually tailored intervention, based on principles of engagement in mental health and family dynamics, is necessary to alleviate disparities for this population.

**Research Question.** Which FN components contribute meaningfully to improvement in access to child mental health services, defined as engagement in mental health service within 90 days after randomization.

**Brief description of the study intervention: A paraprofessional model of family navigation for child behavioral health.** FN is an evidence-based care management strategy designed to reduce disparities in care, and thus, represents a promising strategy to help low income and minority families access timely mental health services. Traditional navigation models utilize trained community health workers who assist families in overcoming systems and patient-specific barriers to a defined set of services over a time-limited period. Navigators - in the proposed study called “Family Partners” (FPs) – are paraprofessionals who share key attributes (cultural, language, lived experience) with the population served. FN is rooted in the Chronic Care Model and has evidence in diseases such as cancer and HIV as a means to reduce disparities by shortening the interval between a positive screen (e.g., a mammogram for breast cancer) and definitive diagnosis. Data from our group and others demonstrate that a

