### 3.2 Rationale and Purpose

**Importance and value of the information to be gained.** Despite significant evidence supporting the effectiveness of FN, concerns exist about the ability to disseminate this intervention to a broad population due to inefficiency and cost. The current proposal is designed to test which FN components are most efficient and effective. This information then guides assembly of an optimized FN model, tailored to low income and racial-ethnic minority families, seen in primary care and in accessing mental health services that achieves the primary outcomes with least resource consumption and participant burden .

**Innovating FN delivery through new methods and technologies.** Our principal innovation involves use of a Multiphase Optimization Strategy (MOST) to identify the most effective FN delivery approaches. Although FN has been previously used successfully across a variety of mental and behavioral health conditions (e.g., ASD and ADHD), we are proposing to use a methodology—one that is conceptually rooted in engineering and that emphasizes efficiency and careful management of resources—to systematically study FN delivery and guide the development of an optimized intervention model of FN for child behavioral health services. At the same time, to promote future spread, we are deliberately testing FN within the Oregon Community Health Information Network (OCHIN), embedded in the HER, OCHIN is a healthcare innovation center designed to promote the dissemination of quality care for all. Use of these methodologies and technologies within the study population offers the opportunity to develop an optimized FN delivery strategy, grounded in empirical data, that can be disseminated and provide a solution for barriers to behavioral health care engagement for traditionally undeserved children and families.

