## 4.2 Study Outcome Measures (See Table 1)

### 4.2.1 Primary Outcome Measures

#### Objective 1: To identify the most effective strategy to deliver FN

**Our primary outcome measure is receipt of behavioral health services within 90 days (yes/no)** will be defined as first encounter with behavioral health services within 90 days of randomization obtained from the electronic health record including Family Partner's template documentation.

Related to this primary objective, we will evaluate *time-to-receipt of behavioral health services* defined as time from randomization to first behavioral health service encounter obtained from the electronic health record, including family partner's template documentation. Dates will be obtained from administrative and billing data (electronic health records) for services within DotHouse, and FP documentation for services outside the health center.

A second primary outcome includes change in child symptoms over time.

- Pediatric Symptom Checklist-17 (PSC-17). A 17-item psychosocial screen designed to recognize cognitive, emotional, and behavioral problems. Three subscale Internalizing, Attention, and Externalizing have specific cutoffs and provide additional guidance regarding need for further follow-up. PSC-17 is embedded in the Epic (electronic health record) as a self-scoring form. It is widely used and has been validated in diverse populations.
- The Survey of Wellbeing of Young Children (SWYC). The SWYC screens for cognitive, motor, language, and social-emotional development among children up to 5½ years of age. We will track behavioral symptoms using the SWYC's Preschool Pediatric Symptom Checklist (PPSC), an 18-item questionnaire that has demonstrated strong concurrent validity with the Child Behavior Checklist (CBCL) and parents' reports of socio-emotional diagnoses as well as acceptability in diverse populations. Translations are available in a range of languages and the SWYC is currently being incorporated into the Epic system used at DotHouse.

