**Table 1. Primary and Secondary Outcomes**

	Outcome	Description	Measurement Source	Timing
Primary	Time to services	Time from randomization to first behavioral health service encounter	Electronic health record including FP's template documentation	90 days
	Access to services	1 st encounter with behavioral health services within 90 days of randomization	Electronic health record including FP's template documentation	90 days
	Child symptoms	Score on PSC-17 and SWYC	Measures will be sent to families via Epic's mobile app MyChart or administered by Zoom/telephone in REDCap or sent to the parent by mail	Baseline 3, 6, 9, & 12 mo
Secondary	Retention in services	≥4 visits or resolution of service need for families receiving psychotherapeutic or psychopharmacological services	Electronic health record including FP's template documentation	90 days
	Patient Satisfaction	HCQ & PSN-I	Measures will be sent to families via Epic's mobile app MyChart or administered by Zoom/ telephone in REDCap or sent by mail	6 mo
	Qualitative Parent Interviews	Parent interviews to describe the effect of cultural and linguistic concordance between patients and FN.	Interview completed through Zoom/phone and audio recorded, stored in HIPPA compliant BOX drive.	6 mo
	Qualitative DotHouse Staff Interviews	DotHouse staff interviews to understand their perspective in the implementation of family navigation (work flow changes etc).	Interview completed through Zoom/phone and audio recorded, stored in HIPPA compliant BOX drive.	ongoing

Note: The PSC-17 is currently administered to children at pediatric well visits at DotHouse as part of usual care. Plans are to implement the SWYC in summer/fall of 2018. Both tools have been used extensively and research supports use for symptom monitoring.

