**Rationale for study design and features.** Specifically, we will use *Multiphase Optimization Strategy (MOST)*, a research method borrowed from the field of engineering, which relies on a randomized, multi-factorial design, and therefore facilitates our ability to simultaneously test the effectiveness of three novel strategies and combinations for delivering FN components. The design will also allow us to test varying combinations of FN factors, ranging from what we propose is the least innovative (core FN) to the most innovative (enhanced technology +community visits +enhanced monitoring). We will then evaluate which combinations of factors are most effective and efficient in regards to achieving the primary outcome (engagement in child mental health services). *This is also a pragmatic experiment.* Similar to pragmatic trials, FN will be integrated into routine clinic workflow and supported by standardized visit templates within the electronic health record which will assist with studying implementation and next steps for dissemination into other primary care and community health centers in the future.

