**Planned variation in intervention strategy.** As seen in figure 3 above, study participants will be assigned to varying combinations of intervention delivery strategies or factorials:

**Strategy A** - Care Coordination (Usual care v. Enhanced: Technology assisted);

**Strategy B** - Mode of Delivery (Clinic-based v. Clinic + Community); and

**Strategy C** - Symptom Tracking (Pediatric Surveillance at annual well-child visit v. Enhanced: Tracking at 3, 6, 9, and 12 months).

**Strategy D:** Visit structure (individually tailored vs standardized, schedule-based visits with families)

**Methods for collecting data for assessment of study objectives.** As seen in **Table 1**, data regarding use of services will be collected and obtained for analysis using the EHR. This EHR data will include FP's template documentation of FN activities, and service use measures (engagement in services measures). Clinical Measures will be sent to families via Epic's mobile app MyChart program, REDCap, administered via telephone or HIPAA compliant Zoom by the study RA or sent to the parent by mail with a return stamped envelope. Once the measures are received by mail, the responses will be manually entered into our RedCap database and the paper copies stored in a locked filing cabinet in a locked office. In cases where families are unable to use MyChart due to limited access to a computer or limited computer literacy and the FP will contact them and enter responses to measures into the appropriate EHR form or mail the parent a copy.

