**Strategy C: Pediatric Surveillance v. Enhanced: Tracking at 3, 6, 9, and 12 months.** In core FN (i.e. Pediatric Surveillance at well-child visits), monitoring is determined by standard pediatric practice. In Massachusetts, behavioral screening is mandated at every pediatric visit, which for children in the target population (ages 3-12 years) is annually. In experimental conditions with "enhanced monitoring," FPs will screen children using validated instruments quarterly (SWYC, PSC-17 based on age) and communicate results to the child's care team. The screening tools will be deployed through MyChart , the EPIC EHR patient portal. Results feed directly into the child's record. Screening tools may also be deployed through REDCap or mailed to the parent in a sealed envelope with a stamped and addressed return envelope inside. Once the mailed parent measures are received by research staff at Boston Medical Center, they will be manually entered into RedCap and the paper copies will be stored in a locked filing cabinet in a locked office. The FP will be responsible for initiating and tracking the screening. She will message the child's PCP when new screening results are available and communicate with the PCP and care team regarding any changes in symptoms. We expect additional costs of increased monitoring to be modest, and that the additional information will allow care to be better aligned with children's symptomatology and, thus, lead to improved engagement with services.

**Strategy D: tailored vs standardized, schedule-based visits with families.** Families who receive tailored visits, will work with their FN on addressing issues as they arise. They will not have any pre-specified schedule for visits or contacts. Families who received standardized scheduled visits, will have a pre-specified schedule of visits. This will include monthly contacts with families for 6 months. Each contact will have a specified agenda which includes review of family goals, and a topic (e.g. what is an individualized education plan) to review.

Regardless of the combination of delivery components to which families are randomized (core or enhanced strategies), families will core FN elements.

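### Enhanced symptom tracking (factor C) is first scheduled at about month 3, just as the 90-day outcome closes, so the 60% v 75% sizing in 12.2 does not hold for C

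*Combined protocol and SAP*

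**What the plan says.** **Factor C.** Section 5 (Planned variation in intervention strategy) sets the levels as "Symptom Tracking (Pediatric Surveillance at annual well-child visit v. Enhanced: Tracking at 3, 6, 9, and 12 months". Section 8 (Strategy C) says of the enhanced level that "FPs will screen children using validated instruments quarterly" and pass the results to the care team. In Appendix A the enhanced-tracking row is marked at baseline and then at months 3, 6, 9 and 12. Section 9 places the baseline measures before randomization, so they are common to both levels. No factor C activity is described between randomization and month 3.

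**Outcome.** The research question in 3.1 defines access as "engagement in mental health service within 90 days after randomization", and 4.2.1 defines the primary outcome as "first encounter with behavioral health services within 90 days of randomization". Section 4.2.1 adds: "A second primary outcome includes change in child symptoms over time". Table 1 also lists time to services, "Time from randomization to first behavioral health service encounter", with timing of 90 days; the text of 4.2.1 and 12.3 sets no such limit on it.

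**Hypothesis, sizing and analysis.** Section 12.1 expects enhanced tracking to beat surveillance for access, without naming a window. Section 12.2 sizes the trial on 90-day receipt: 60% under core navigation against 75% under any delivery condition, two-sided 5%, 304 families. Section 12.3 tests the strategies' main effects on 90-day receipt by logistic regression, followed by Cox and multiple-services models, and under Objective 2 names C among the strategies tested.

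**Use of the result.** Section 5 will judge "which combinations of factors are most effective and efficient in regards to achieving the primary outcome"; section 3.2 seeks a model "that achieves the primary outcomes with least resource consumption and participant burden".

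**The concern.** A factor can change an outcome only after its levels begin to differ. Enhanced tracking works, by the account in section 8, through a screen, a message to the primary care clinician, and better-aligned care. On the written schedule the first of those steps comes when the 90-day window is over or nearly over. The 15-point difference assumed in 12.2 then has almost no time in which to arise for C.

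What is at stake is the reading of the result. C is one of the four strategies in the primary objective. Combinations are compared on the primary outcome, with cost and burden also weighed. A null for C on 90-day receipt is what the schedule predicts whether or not tracking helps families later, and nothing in the plan tells the reader so.

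**Working it through.** **Inputs.** From 12.2: 60% v 75%, two-sided 5%, 304 families. Two levels per factor gives 152 v 152. Window of 90 days (4.2.1). First enhanced screen at month 3 (section 5, Appendix A). Power for this outcome is not stated; 80% is assumed. Follow-up in the EHR is 12 months (Protocol Summary).

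**1. The plan's own figure.** Two proportions, pooled variance, mean proportion 0.675:

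n per level = [1.960 × √(2 × 0.675 × 0.325) + 0.842 × √(0.60 × 0.40 + 0.75 × 0.25)]² / 0.15² = 151.9, so 152 per level and 304 in total. The arithmetic of 12.2 reproduces, and 152 v 152 gives 80.0% power.

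**2. Time left in the window.** One quarter is 365.25 / 4 = 91.3 days. A month 3 screen leaves no days before day 90.

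**3. Power for C if the screen comes earlier.** With a constant hazard to day 90, the daily rates are −ln(0.40)/90 = 0.01018 (core) and −ln(0.25)/90 = 0.01540 (enhanced), a hazard ratio (HR) of 1.513. If C acts at once from day s, then

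90-day receipt = 1 − exp[−0.01018 × s − 0.01018 × HR × (90 − s)].

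| First screen | Receipt, HR 1.513 | Power v 60% | Receipt, HR 2 | Power v 60% |
|---|---|---|---|---|
| Day 60 | 65.8% | 18.1% | 70.5% | 48.7% |
| Day 75 | 63.0% | 8.4% | 65.7% | 17.5% |
| Day 80 | 62.0% | 6.5% | 63.9% | 10.7% |
| Day 90 or later | 60.0% | 5.0% | 60.0% | 5.0% |

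The 5% is the false-positive rate. The earlier days matter because no window is given for the month 3 screen, and because Appendix A marks randomization at both baseline and month 1, so the time origin is unclear.

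**4. What the planned 12-month follow-up could show.** At day 90 between 304 × 0.25 = 76 and 304 × 0.40 = 122 families are still unserved. Let C act from day 90 to day 365 at HR 1.513. Power ≈ Φ(√events / 2 × ln 1.513 − 1.96). The hazard after day 90 is not in the documents, so a range is assumed.

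| Hazard after day 90, share of core | Unserved at day 90 | Events | Power |
|---|---|---|---|
| 100% | 122 | 117 | 0.61 |
| 25% | 76 | 44 | 0.28 |
| 10% | 122 | 36 | 0.24 |
| 10% | 76 | 22 | 0.165 |

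**5. One Cox effect for C over the whole year.** A simulation (5,000 trials per scenario, 304 families, no effect of C before day 90, HR 1.513 after, hazard after day 90 at 25–100% of core) gives 8–27% power for a single C term, with a mean hazard ratio of 1.07–1.17. A separate C term from day 90 gives 27–59% power and recovers 1.51–1.53. The single term averages in the months when the levels were the same.

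**6. The symptom-measure schedules, side by side.**

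| Place | Standard level of C |
|---|---|
| Section 5 | Annual well-child visit |
| Appendix A, TAU row | Baseline, months 6 and 12 |
| Table 1, followed by section 9 | Baseline, 3, 6, 9 and 12 months, all families, no restriction by C |

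If Table 1 governs, both levels complete the same instruments at month 3, and the remaining contrast is mainly the Family Partner starting the screen and messaging the care team. The documents do not settle which schedule applies.

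**The case against.** The strongest reply is that a null for C on 90-day receipt is still a valid intention-to-treat answer. The research question is about 90 days, and quarterly tracking as scheduled may truly add little to 90-day access. That stands. A reader might infer from the timing that such a null is no evidence against C at all. The documents do not support so broad a reading: the null bears on 90-day access and is silent only on what happens after month 3.

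Second, C is not confined to 90-day receipt. Symptom change to 12 months is a second primary outcome, and 12.3 plans Cox and multiple-services models. This also stands, but none of these is sized for C, and Table 1 appears to cut time to services at 90 days.

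Third, some first screens may come early, and Family Partners know the assignment, so an earlier indirect effect is possible. No such effect is described. A screen at day 60, a month early, still gives only 18% power at the planning effect, and the calculation favours the plan by letting C act immediately.

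Fourth, a reader might infer that the plan would discard C after a null 90-day result. It contains no such rule.

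**Conclusion.** The concern holds for the sizing claim. On the documented schedule, 60% v 75% within 90 days does not apply to C: the chance of a significant C effect is about 5% if the first screen is at or after day 90, and 6.5–18% if it falls between day 80 and day 60 (HR 1.51), against 80% for a factor acting throughout. This rests on a constant hazard to day 90, an immediate effect of C, and the assumed 80%. A null could not be separated from timing.

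The total of 304 is not wrong, and this timing leaves A, B and D untouched. Nor do the documents make a post-day-90 Cox analysis the necessary main analysis for C; it is one reasonable option, with low precision that depends on a hazard they do not give. With no decision rule hanging on the 90-day null and later analyses of C already planned, this is something that should be fixed rather than a defect that undermines the trial.

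**What to change.** Keep C in the factorial model, and:

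1. State in 12.2 that the 60% v 75% calculation does not cover C. State in 12.3 that a null for C on 90-day receipt describes 90-day access only and is uninformative about effects after month 3.
2. Reconcile the symptom-measure schedule for standard C across section 5, Table 1 with section 9, and Appendix A. State what distinguishes the two levels, and the time origin and window of the month 3 screen.
3. Reconcile the 90-day timing of time to services in Table 1 with 4.2.1 and 12.3.
4. In the planned Cox model, run through the 12-month EHR follow-up, add a separate C effect from the day the first enhanced screen can occur. Report it as a supportive estimate with a 95% confidence interval, beside the 90-day result and the 12-month symptom outcome.
5. Date the amendment and make it without knowledge of results by factor. The protocol is at Version 1.2 (September 2023), and the DSMB Charter provides for six-monthly interim analyses of the primary end point and closed sessions that the investigators may attend.

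The cost is amended text and one time-dependent term, on data already to be collected. The downside is low precision for C: about 28–61% power at HR 1.51 if the hazard after day 90 is 25–100% of the core rate, and about 16–24% if it is 10%. C would be estimated, not confirmed.

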**Assessment of fidelity to the Family Navigation core model and delivery strategies.**

An important component of the procedures includes training of the family partners and assurance of fidelity. After completing a manualized training curriculum, we will assess fidelity to the Family Navigation model using methods employed in our ongoing navigation study (as well as two additional prior FN studies) and adapted for the current study. To assess content fidelity, we will adapt our Navigation Fidelity Checklist (NFC) to rate adherence to the 6 key components of the Family Navigation intervention outlined in our proposal: identification of family preferences for behavioral health services; support for access to behavioral health services, promoting engagement in evidence-based treatment; monitoring of family goals; family strengthening, and connection to concrete resources.

Adherence to the core components and the assigned FN delivery condition will be evaluated through review of structured navigation visit templates integrated into the electronic health record, FP contact logs, and via review of a randomly selected session between the FP and each patient that will be audio recorded for fidelity purposes. A random sample of 2 visits per month for each FP will be reviewed using the Navigation Checklist. In addition, the project manager will review reports of data abstracted from the electronic health record and the FP contact logs monthly to monitor possible contamination among study conditions. The integration of MI techniques into interactions between FPs and participating families will be assessed using audio recordings of sessions between the FP and parent. The interactions will be scored using the Motivational Interviewing Treatment Integrity (MITI), a measure validated for use in training

and supervision in implementing MI. In order to support ongoing fidelity, FPs will meet bi-weekly with their supervisor and [name] (a co-investigator and child psychiatrist at DotHouse) to review cases. If a FP is not meeting fidelity criteria, they will be provided with retraining and additional support. Once per year, FP will participate in an MI booster training session to maintain their MI skills.

